	730.04 + 041.2	Acute osteomyelitis, hand + pneumococcus	M86.041 + B95.3 M86.042 + B95.3 M86.049 + B95.3 M86.141 + B95.3 M86.142 + B95.3 M86.149 + B95.3 M86.241 + B95.3 M86.242 + B95.3 M86.249 + B95.3	Acute hematogenous osteomyelitis, right hand + Streptococcus pneumoniae Acute hematogenous osteomyelitis, left hand + Streptococcus pneumoniae Acute hematogenous osteomyelitis, unspecified hand + Streptococcus pneumoniae Other acute osteomyelitis, right hand + Streptococcus pneumoniae Other acute osteomyelitis, left hand + Streptococcus pneumoniae Other acute osteomyelitis, unspecified hand + Streptococcus pneumoniae Subacute osteomyelitis, right hand + Streptococcus pneumoniae Subacute osteomyelitis, left hand + Streptococcus pneumoniae Subacute osteomyelitis, unspecified hand + Streptococcus pneumoniae
	730.05 + 041.2	Acute osteomyelitis, pelvic region and thigh + pneumococcus	M86.051 + B95.3 M86.052 + B95.3 M86.059 + B95.3 M86.151 + B95.3 M86.152 + B95.3 M86.159 + B95.3 M86.251 + B95.3 M86.252 + B95.3 M86.259 + B95.3	Acute hematogenous osteomyelitis, right femur + Streptococcus pneumoniae Acute hematogenous osteomyelitis, left femur + Streptococcus pneumoniae Acute hematogenous osteomyelitis, unspecified femur + Streptococcus pneumoniae Other acute osteomyelitis, right femur + Streptococcus pneumoniae Other acute osteomyelitis, left femur + Streptococcus pneumoniae Other acute osteomyelitis, unspecified femur + Streptococcus pneumoniae Subacute osteomyelitis, right femur + Streptococcus pneumoniae Subacute osteomyelitis, left femur + Streptococcus pneumoniae Subacute osteomyelitis, unspecified femur + Streptococcus pneumoniae
	730.06 + 041.2	Acute osteomyelitis, lower leg + pneumococcus	M86.061 + B95.3 M86.062 + B95.3 M86.069 + B95.3 M86.161 + B95.3	Acute hematogenous osteomyelitis, right tibia and fibula + Streptococcus pneumoniae Acute hematogenous osteomyelitis, left tibia and fibula + Streptococcus pneumoniae Acute hematogenous osteomyelitis, unspecified tibia and fibula + Streptococcus pneumoniae

PFIZER CONFIDENTIAL

CT24-WI-GL02-RF02 5.0 Non-Interventional Study Protocol Template For Secondary Data Collection Study 01-Aug-2023

Page 36 of 46

			M86.162 + B95.3 M86.169 + B95.3 M86.261 + B95.3 M86.262 + B95.3 M86.269 + B95.3	Other acute osteomyelitis, right tibia and fibula + Streptococcus pneumoniae Other acute osteomyelitis, left tibia and fibula + Streptococcus pneumoniae Other acute osteomyelitis, unspecified tibia and fibula + Streptococcus pneumoniae Subacute osteomyelitis, right tibia and fibula + Streptococcus pneumoniae Subacute osteomyelitis, left tibia and fibula + Streptococcus pneumoniae Subacute osteomyelitis, unspecified tibia and fibula + Streptococcus pneumoniae
730.07 + 041.2	Acute osteomyelitis, ankle and foot + pneumococcus	M86.071 + B95.3 M86.072 + B95.3 M86.079 + B95.3 M86.171 + B95.3 M86.172 + B95.3 M86.179 + B95.3 M86.271 + B95.3 M86.272 + B95.3 M86.279 + B95.3	Acute hematogenous osteomyelitis, right ankle and foot + Streptococcus pneumoniae Acute hematogenous osteomyelitis, left ankle and foot + Streptococcus pneumoniae Acute hematogenous osteomyelitis, unspecified ankle and foot + Streptococcus pneumoniae Other acute osteomyelitis, right ankle and foot + Streptococcus pneumoniae Other acute osteomyelitis, left ankle and foot + Streptococcus pneumoniae Other acute osteomyelitis, unspecified ankle and foot + Streptococcus pneumoniae Subacute osteomyelitis, right ankle and foot + Streptococcus pneumoniae Subacute osteomyelitis, left ankle and foot + Streptococcus pneumoniae Subacute osteomyelitis, unspecified ankle and foot + Streptococcus pneumoniae	
730.08 + 041.2	Acute osteomyelitis, other specified sites + pneumococcus	M86.08 + B95.3 M86.18 + B95.3 M86.28 + B95.3	Acute hematogenous osteomyelitis, other sites + Streptococcus pneumoniae Other acute osteomyelitis, other site + Streptococcus pneumoniae Subacute osteomyelitis, other site + Streptococcus pneumoniae	
730.09 + 041.2	Acute osteomyelitis, multiple sites + pneumococcus	M86.09 + B95.3 M86.19 + B95.3 M86.29 + B95.3	Acute hematogenous osteomyelitis, multiple sites + Streptococcus pneumoniae Other acute osteomyelitis, multiple sites + Streptococcus pneumoniae Subacute osteomyelitis, multiple sites + Streptococcus pneumoniae	
730.2 + 041.2 730.21 + 041.2 730.22 + 041.2 730.23 + 041.2 730.24 + 041.2 730.25 + 041.2 730.26 + 041.2 730.27 + 041.2 730.29 + 041.2	Unspecified osteomyelitis, site unspecified + pneumococcus Unspecified osteomyelitis, shoulder region + pneumococcus Unspecified osteomyelitis, upper arm + pneumococcus Unspecified osteomyelitis, forearm + pneumococcus Unspecified osteomyelitis, hand + pneumococcus Unspecified osteomyelitis, pelvic region and thigh + pneumococcus Unspecified osteomyelitis, lower leg + pneumococcus Unspecified osteomyelitis, ankle and foot + pneumococcus Unspecified osteomyelitis, multiple sites + pneumococcus	M86.9 + B95.3	Osteomyelitis, unspecified + Streptococcus pneumoniae	

PFIZER CONFIDENTIAL

CT24-WI-GL02-RF02 5.0 Non-Interventional Study Protocol Template For Secondary Data Collection Study 01-Aug-2023

Page 37 of 46

	730.28 + 041.2	Unspecified osteomyelitis, other specified sites + pneumococcus	M46.20 + B95.3 M46.21 + B95.3 M46.22 + B95.3 M46.23 + B95.3 M46.24 + B95.3 M46.25 + B95.3 M46.26 + B95.3 M46.27 + B95.3 M46.28 + B95.3	Osteomyelitis of vertebra, site unspecified + Streptococcus pneumoniae Osteomyelitis of vertebra, occipito-atlanto-axial region + Streptococcus pneumoniae Osteomyelitis of vertebra, cervical region + Streptococcus pneumoniae Osteomyelitis of vertebra, cervicothoracic region + Streptococcus pneumoniae Osteomyelitis of vertebra, thoracic region + Streptococcus pneumoniae Osteomyelitis of vertebra, thoracolumbar region + Streptococcus pneumoniae Osteomyelitis of vertebra, lumbar region + Streptococcus pneumoniae Osteomyelitis of vertebra, lumbosacral region + Streptococcus pneumoniae Osteomyelitis of vertebra, sacral and sacrococcygeal region + Streptococcus pneumoniae
Pneumonia				
All-Cause	480-486 487.0			Viral, bacterial, unspecified pneumonia
	480	Pneumonia due to adenovirus	J12.0	Adenoviral pneumonia
	480.1	Pneumonia due to respiratory syncytial virus	J12.1	Respiratory syncytial virus pneumonia
	480.2	Pneumonia due to parainfluenza virus	J12.2	Parainfluenza virus pneumonia
	480.3	Pneumonia due to SARS-associated coronavirus	J12.81 J12.82	Pneumonia due to SARS-associated coronavirus Pneumonia due to coronavirus disease 2019
	480.8	Pneumonia due to other virus not elsewhere classified	J12.3 J12.89	Human metapneumovirus pneumonia Other viral pneumonia
	480.9	Viral pneumonia, unspecified	J12.9	Viral pneumonia, unspecified
	481	Pneumococcal pneumonia [Streptococcus pneumoniae pneumonia]	J18.1 J13	Lobar pneumonia, unspecified organism Pneumonia due to Streptococcus pneumoniae
	482	Pneumonia due to Klebsiella pneumoniae	J15.0	Pneumonia due to Klebsiella pneumoniae
	482.1	Pneumonia due to Pseudomonas	J15.1	Pneumonia due to Pseudomonas
	482.2	Pneumonia due to Hemophilus influenzae [H. influenzae]	J14	Pneumonia due to Hemophilus influenzae
	482.3	Pneumonia due to Streptococcus , unspecified	J15.4	Pneumonia due to other streptococci
	482.31	Pneumonia due to Streptococcus , group A	J15.4	Pneumonia due to other streptococci
	482.32	Pneumonia due to Streptococcus , group B	J15.3	Pneumonia due to Streptococcus , group B
	482.39	Pneumonia due to other Streptococcus	J15.4	Pneumonia due to other streptococci

PFIZER CONFIDENTIAL

CT24-WI-GL02-RF02 5.0 Non-Interventional Study Protocol Template For Secondary Data Collection Study 01-Aug-2023

Page 38 of 46

	482.4	Pneumonia due to Staphylococcus, unspecified	J15.20	Pneumonia due to staphylococcus, unspecified
	482.41	Methicillin susceptible pneumonia due to Staphylococcus aureus	J15.211	Pneumonia due to Methicillin susceptible Staphylococcus aureus
	482.42	Methicillin resistant pneumonia due to Staphylococcus aureus	J15.212	Pneumonia due to Methicillin resistant Staphylococcus aureus
	482.49	Other Staphylococcus pneumonia	J15.29	Pneumonia due to other staphylococcus
	482.81	Pneumonia due to anaerobes	J15.8	Pneumonia due to other specified bacteria
	482.82	Pneumonia due to escherichia coli [E. coli]	J15.5	Pneumonia due to Escherichia coli
	482.83	Pneumonia due to other gram-negative bacteria	J15.6	Pneumonia due to other aerobic Gram-negative bacteria
	482.84	Pneumonia due to Legionnaires' disease	A48.1	Legionnaires' disease
	482.89	Pneumonia due to other specified bacteria	J15.8	Pneumonia due to other specified bacteria
	482.9	Bacterial pneumonia, unspecified	J15.9	Unspecified bacterial pneumonia
	483	Pneumonia due to mycoplasma pneumoniae	J15.7	Pneumonia due to Mycoplasma pneumoniae
	483.1	Pneumonia due to chlamydia	J16.0	Chlamydial pneumonia
	483.8	Pneumonia due to other specified organism	J16.8	Pneumonia due to other specified infectious organisms
	484.1	Pneumonia in cytomegalic inclusion disease	B25.0	Cytomegaloviral pneumonitis
	484.3	Pneumonia in whooping cough	A37.91 A37.01 A37.11 A37.81	Whooping cough, unspecified species with pneumonia Whooping cough due to Bordetella pertussis with pneumonia Whooping cough due to Bordetella parapertussis with pneumonia Whooping cough due to other Bordetella species with pneumonia
	484.5	Pneumonia in anthrax	A22.1	Pulmonary anthrax
	484.6	Pneumonia in aspergillosis	B44.0	Invasive pulmonary aspergillosis
	484.7	Pneumonia in other systemic mycoses	J17	Pneumonia in diseases classified elsewhere
	484.8	Pneumonia in other infectious diseases classified elsewhere	J17 B77.81	Pneumonia in diseases classified elsewhere Ascariasis pneumonia
	485	Bronchopneumonia, organism unspecified	J18.0	Bronchopneumonia, unspecified organism

PFIZER CONFIDENTIAL

CT24-WI-GL02-RF02 5.0 Non-Interventional Study Protocol Template For Secondary Data Collection Study 01-Aug-2023

Page 39 of 46

	486	Pneumonia, organism unspecified	J18.8 J18.9	Other pneumonia, unspecified organism Pneumonia, unspecified organism
	487	Influenza with pneumonia	J10.00 J10.08 J11.00 J11.08 J12.9	Influenza due to other identified influenza virus with unspecified type of pneumonia Influenza due to other identified influenza virus with other specified pneumonia Influenza due to unidentified influenza virus with unspecified type of pneumonia Influenza due to unidentified influenza virus with specified pneumonia Viral pneumonia, unspecified
	510.x			Empyema
	510	Empyema with fistula	J86.0	Pyothorax with fistula
	510.9	Empyema without mention of fistula	J86.9	Pyothorax without fistula
			J85.1	Abscess of lung with pneumonia
	136.3	Pneumocystosis	B59	Pneumocystosis
Pneumococca 1	481	Pneumococcal pneumonia	J13	Pneumonia due to Streptococcus pneumoniae
	482.9 + 041.2	Bacterial pneumonia, unspecified + pneumococcus	J15.9 + B95.3	Unspecified bacterial pneumonia + Streptococcus pneumoniae
	485 + 041.2	Bronchopneumonia, organism unspecified + pneumococcus	J18.0 + B95.3	Bronchopneumonia, unspecified organism + Streptococcus pneumoniae
	486 + 041.2	Pneumonia, organism unspecified + pneumococcus	J18.8 + B95.3 J18.9 + B95.3	Other pneumonia, unspecified organism + Streptococcus pneumoniae Pneumonia, unspecified organism + Streptococcus pneumoniae
	510.x + 041.2			Empyema + pneumococcus
	510 + 041.2	Empyema with fistula + pneumococcus	J86.0 + B95.3	Pyothorax with fistula + Streptococcus pneumoniae
	510.9 + 041.2	Empyema without mention of fistula + pneumococcus	J86.9 + B95.3	Pyothorax without fistula + Streptococcus pneumoniae

PFIZER CONFIDENTIAL

CT24-WI-GL02-RF02 5.0 Non-Interventional Study Protocol Template For Secondary Data Collection Study 01-Aug-2023

Page 40 of 46

Table 6. National Drug Codes and Procedure Codes for Identifying Immunosuppressive Medications (see excel)

Table 7. National Drug Codes and Procedure Codes for Identifying Influenza Vaccinations (see excel)

Table 8. National Drug Codes and CPT® Codes for Identifying PPSV23 Vaccination

Code	Type	Description
90732	CPT	Pneumovax 23
00006473900	NDC	Pneumovax 23
00006473901	NDC	Pneumovax 23
00006473950	NDC	Pneumovax 23
00006474100	NDC	Pneumovax 23
00006483701	NDC	Pneumovax 23
00006483702	NDC	Pneumovax 23
00006483703	NDC	Pneumovax 23
00006489400	NDC	Pneumovax 23
00006489400	NDC	Pneumovax 23
00006494300	NDC	Pneumovax 23
00006494301	NDC	Pneumovax 23
00247040201	NDC	Pneumovax 23
50090145200	NDC	Pneumovax 23
50090145209	NDC	Pneumovax 23
54569141200	NDC	Pneumovax 23
54569653800	NDC	Pneumovax 23
54868333901	NDC	Pneumovax 23
54868333909	NDC	Pneumovax 23
54868432000	NDC	Pneumovax 23
54868432009	NDC	Pneumovax 23
55045354202	NDC	Pneumovax 23
00005230931	NDC	Pnu-Imune 23
00005230933	NDC	Pnu-Imune 23
54868070700	NDC	Pnu-Imune 23

Table 9. CPT® codes to identify CD4 laboratory tests

Code	Type	Description
86361	CPT	Absolute CD4 count
86360	CPT	Absolute CD4 and CD8 counts with ratio

Table 10. CPT® codes to identify viral load laboratory tests

Code	Type	Description
87534	CPT	Infectious agent detection by nucleic acid (DNA or RNA); HIV-1, direct probe technique
87535	CPT	Infectious agent detection by nucleic acid (DNA or RNA); HIV-1, amplified probe technique
87536	CPT	Infectious agent detection by nucleic acid (DNA or RNA); HIV-1, quantification

Table 11. Diagnosis Codes for Identifying All-Cause Pneumonia not due to HIV

Condition	ICD-9-CM		ICD-10-CM		
	Codes	Description	Codes	Description	
		Viral, bacterial, unspecified pneumonia			
All-Cause	480-486 487.0				
	480	Pneumonia due to adenovirus	J12.0	Adenoviral pneumonia	
	480.1	Pneumonia due to respiratory syncytial virus	J12.1	Respiratory syncytial virus pneumonia	
	480.2	Pneumonia due to parainfluenza virus	J12.2	Parainfluenza virus pneumonia	
	480.3	Pneumonia due to SARS-associated coronavirus	J12.81 J12.82	Pneumonia due to SARS-associated coronavirus Pneumonia due to coronavirus disease 2019	
	480.8	Pneumonia due to other virus not elsewhere classified	J12.3 J12.89	Human metapneumovirus pneumonia Other viral pneumonia	
	480.9	Viral pneumonia, unspecified	J12.9	Viral pneumonia, unspecified	
	481	Pneumococcal pneumonia [Streptococcus pneumoniae pneumonia]	J18.1 J13	Lobar pneumonia, unspecified organism Pneumonia due to Streptococcus pneumoniae	
	482	Pneumonia due to Klebsiella pneumoniae	J15.0	Pneumonia due to Klebsiella pneumoniae	
	482.1	Pneumonia due to Pseudomonas	J15.1	Pneumonia due to Pseudomonas	
	482.2	Pneumonia due to Hemophilus influenzae [H. influenzae]	J14	Pneumonia due to Hemophilus influenzae	
	482.3	Pneumonia due to Streptococcus, unspecified	J15.4	Pneumonia due to other streptococci	
	482.31	Pneumonia due to Streptococcus, group A	J15.4	Pneumonia due to other streptococci	
	482.32	Pneumonia due to Streptococcus, group B	J15.3	Pneumonia due to streptococcus, group B	
	482.39	Pneumonia due to other Streptococcus	J15.4	Pneumonia due to other streptococci	
	482.4	Pneumonia due to Staphylococcus, unspecified	J15.20	Pneumonia due to staphylococcus, unspecified	
	482.41	Methicillin susceptible pneumonia due to Staphylococcus aureus	J15.211	Pneumonia due to Methicillin susceptible Staphylococcus aureus	

PFIZER CONFIDENTIAL

CT24-WI-GL02-RF02 5.0 Non-Interventional Study Protocol Template For Secondary Data Collection Study 01-Aug-2023

Page 43 of 46

482.42	Methicillin resistant pneumonia due to Staphylococcus aureus	J15.212	Pneumonia due to Methicillin resistant Staphylococcus aureus
482.49	Other Staphylococcus pneumonia	J15.29	Pneumonia due to other staphylococcus
482.81	Pneumonia due to anaerobes	J15.8	Pneumonia due to other specified bacteria
482.82	Pneumonia due to escherichia coli [E. coli]	J15.5	Pneumonia due to Escherichia coli
482.83	Pneumonia due to other gram-negative bacteria	J15.6	Pneumonia due to other aerobic Gram-negative bacteria
482.84	Pneumonia due to Legionnaires' disease	A48.1	Legionnaires' disease
482.89	Pneumonia due to other specified bacteria	J15.8	Pneumonia due to other specified bacteria
482.9	Bacterial pneumonia, unspecified	J15.9	Unspecified bacterial pneumonia
483.1	Pneumonia due to chlamydia	J16.0	Chlamydial pneumonia
483.8	Pneumonia due to other specified organism	J16.8	Pneumonia due to other specified infectious organisms
484.3	Pneumonia in whooping cough	A37.91 A37.01 A37.11 A37.81	Whooping cough, unspecified species with pneumonia Whooping cough due to Bordetella pertussis with pneumonia Whooping cough due to Bordetella parapertussis with pneumonia Whooping cough due to other Bordetella species with pneumonia
484.5	Pneumonia in anthrax	A22.1	Pulmonary anthrax
		J17	Pneumonia in diseases classified elsewhere
484.8	Pneumonia in other infectious diseases classified elsewhere	J17 B77.81	Pneumonia in diseases classified elsewhere Ascariasis pneumonia
485	Bronchopneumonia, organism unspecified	J18.0	Bronchopneumonia, unspecified organism
486	Pneumonia, organism unspecified	J18.8 J18.9	Other pneumonia, unspecified organism Pneumonia, unspecified organism
487	Influenza with pneumonia	J10.00 J10.08 J11.00 J11.08 J12.9	Influenza due to other identified influenza virus with unspecified type of pneumonia Influenza due to other identified influenza virus with other specified pneumonia Influenza due to unidentified influenza virus with unspecified type of pneumonia Influenza due to unidentified influenza virus with specified pneumonia Viral pneumonia, unspecified

510.x		Empyema		
510	Empyema with fistula	J86.0	Pyothorax with fistula	
510.9	Empyema without mention of fistula	J86.9	Pyothorax without fistula	
		J85.1	Abscess of lung with pneumonia	

Table 12. National Drug Codes and CPT® Codes for Identifying Recombinant Zoster Vaccination

Code	Type	Description
58160082801	NDC	Shingrix
58160082803	NDC	Shingrix
50090514700	NDC	Shingrix
58160081912	NDC	Shingrix
58160082311	NDC	Shingrix
50090337200	NDC	Shingrix
90750	CPT	Zoster Vaccine Recombinant, Adjuvanted, Suspension for Intramuscular Injection

Table 13. National Drug Codes for Identifying Candidiasis Antifungals (see excel)

Table 14. Diagnosis Codes for Identifying Opportunistic Infections (see excel)

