There has been a longstanding recommendation for pneumococcal vaccination for PLWH in the United States. PCV13 was recommended for PLWH in 2012 and the uptake in PLWH is higher compared with individuals with other risk conditions [22, 23]; this allows us to examine PCV13 VE in the PLWH population over time. Given the lack of PCV13 VE data in immunocompromised adults, this study was designed to estimate PCV13 VE against pneumococcal disease in PLWH aged ≥ 18 years, overall and, if feasible, at 3, 5, and 7 years after vaccination. In addition to IPD and pneumococcal pneumonia, we will include all-cause pneumonia as a disease endpoint in the analysis, because *S. pneumoniae* is the most common bacterial cause of all-cause pneumonia [24].

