9. RESEARCH METHODS

9.1. Study Design

The VE study will be a retrospective cohort study using health care administrative claims and laboratory data (Figure 1).

PLWH will be identified using administrative claims and include individuals with at least one inpatient International Classification of Diseases, Ninth Revision, Clinical Modification (ICD-9-CM) or International Classification of Diseases, Tenth Revision, Clinical Modification (ICD-10-CM) code related to HIV (Appendix Table 1) or at least 2 outpatient ICD-9-CM or ICD-10-CM codes related to HIV at least 30 days, but no more than 730 days apart, during January 1, 2014 and

PFIZER CONFIDENTIAL

December 31, 2021. PLWH are required to have at least six months of continuous enrollment in one or more health plans and pharmacy benefits after their first HIV-related ICD-9-CM or ICD-10-CM code. These six months of continuous enrollment will be considered the baseline period, during which baseline covariates including demographics, comorbidities, and preventative care will be measured. The baseline period was also selected to minimize the number of outcome events that existed prior to or triggered an HIV diagnosis.

The date following the last date of the baseline period will be defined as the index date. The end of the study will occur on the last date that administrative claims data will be available, September 30, 2022.

For PLWH who receive PCV13 after their index date, we will include the time between their index date and the 13 days after their PCV13 vaccination date as unvaccinated follow-up time. Any outcomes occurring during this time will be counted as events in the unvaccinated cohort. Follow-up that occurs 14 days or more after PCV13 vaccination will be defined as vaccinated follow-up time.

Unvaccinated (no PCV13) PLWH will be followed from index date until the earliest occurrence of the following: 13 days after PCV13 vaccination, death, end of health plan enrollment, or end of study period. Vaccinated PLWH will be followed from 14 days after their PCV13 vaccination, or index date if they were vaccinated during the baseline period, until the earliest occurrence of the following: death, end of health plan enrollment, or end of study period.

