16. APPENDIX

Table 1. Diagnosis Codes for Identifying HIV infection

Code	Type	Description
042	ICD-9-CM	HIV-1 infection
V08	ICD-9-CM	Asymptomatic HIV disease
B20	ICD-10-CM	HIV-1 infection
Z21	ICD-10-CM	Asymptomatic HIV disease

Table 2. National Drug Codes for Identifying HIV Antiretrovirals (see excel)

Table 3. National Drug Codes and CPT® Codes for Identifying PCV13 Vaccination

Code	Type	Description
50090194409	NDC	13-valent pneumococcal conjugate vaccine
54569661300	NDC	13-valent pneumococcal conjugate vaccine

PFIZER CONFIDENTIAL

CT24-WI-GL02-RF02 5.0 Non-Interventional Study Protocol Template For Secondary Data Collection Study

01-Aug-2023

Page 29 of 46

50090194400	NDC	13-valent pneumococcal conjugate vaccine
00005197105	NDC	13-valent pneumococcal conjugate vaccine
00005197104	NDC	13-valent pneumococcal conjugate vaccine
00005197102	NDC	13-valent pneumococcal conjugate vaccine
00005197101	NDC	13-valent pneumococcal conjugate vaccine
90670	CPT	13-valent pneumococcal conjugate vaccine

Table 5. Diagnosis Codes for Identifying Pneumococcal Pneumonia and Pneumonia with Unspecified Causes

Condition	ICD-9-CM		ICD-10-CM	
	Codes	Description	Codes	Description
Pneumococcal pneumonia	481	Pneumococcal pneumonia	J13	Pneumonia due to Streptococcus pneumoniae
	482.9 + 041.2	Bacterial pneumonia, unspecified + pneumococcus	J15.9 + B95.3	Unspecified bacterial pneumonia + Streptococcus pneumoniae
	485 + 041.2	Bronchopneumonia, organism unspecified + pneumococcus	J18.0 + B95.3	Bronchopneumonia, unspecified organism + Streptococcus pneumoniae
	486 + 041.2	Pneumonia, organism unspecified + pneumococcus	J18.8 + B95.3 J18.9 + B95.3	Other pneumonia, unspecified organism + Streptococcus pneumoniae Pneumonia, unspecified organism + Streptococcus pneumoniae
	510.x + 041.2			Empyema + pneumococcus
	510 + 041.2	Empyema with fistula + pneumococcus	J86.0 + B95.3	Pyothorax with fistula + Streptococcus pneumoniae
	510.9 + 041.2	Empyema without mention of fistula + pneumococcus	J86.9 + B95.3	Pyothorax without fistula + Streptococcus pneumoniae
Pneumonia with unspecified causes	480-486 487.0			Viral, bacterial, unspecified pneumonia
	480.9	Viral pneumonia, unspecified	J12.9	Viral pneumonia, unspecified
	482.9	Bacterial pneumonia, unspecified	J15.9	Unspecified bacterial pneumonia
	485	Bronchopneumonia, organism unspecified	J18.0	Bronchopneumonia, unspecified organism

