#### **5.8.7. Vaccine Effectiveness**

Crude PCV13 VE percentages will be estimated based on  $(1-HR) \times 100$ , where HR is obtained from unadjusted Cox models for first episodes for each outcome. VE percentages will also be obtained from marginal structural Cox models (Cox-MSM) after applying the IPT and the IPT\*IPC weights. As the numerators for the stabilized weights will include the index-fixed covariates, those covariates will also be included in the Cox-MSM for the outcomes [9]. Cluster robust standard errors will be used to account for the multiple records per patient. The proportional hazards assumption will be assessed graphically with the inspection of Schoenfeld residuals.

To explore potential changes in VE over time, HRs may also be generated during specific time periods using piecewise Cox models. The time periods will be 0-3 years (0 to 1079 days), 3-5 years (1080 to 1799 days), 5-7 years (1800 to 2549 days).

VE may also be assessed for recurrent events using the Andersen-Gill (AG) model [11]. For each outcome, subsequent events will be of the same type, e.g., in the analysis of IPD it will be assumed that a patient is only at risk for future IPD events. The VE is assumed constant across the recurrent events.

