#### 5.8.11. Analysis of Study Objectives

Crude HRs for PCV13 vaccination and the corresponding VE percentages will be presented together with 95% CIs for each study outcome overall and again during specific time periods (0-3, 3-5, 5-7 years). This will be done for first events and again including recurrent events. Analysis will be repeated using Cox-MSM after applying IPT and the IPT\*IPC weights.

The above analysis will be repeated by the subgroups stated in Section **Error! Reference source not found..**

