#### 5.8.12. Analysis of Negative Control Outcomes and Exposure

The number of patients with the negative control outcome(s) will be presented by PCV13 vaccination status at the time of occurrence. Crude incidence rates and 95% CIs will be presented by PCV13 status for first and recurrent (separated by at least 90 days) episodes. Unadjusted and Cox-MSM will be used to obtain crude and weighted VE estimates and 95% CIs of PCV13 on candidiasis.

The number of patients who receive at least one dose of RZV by the end of the overall follow-up will be reported. Patients will be considered vaccinated with RZV 14 days after their vaccination date. Unadjusted and Cox-MSM will be used to obtain crude and weighted VE estimates and 95% CIs of RZV on each of the study outcomes of interest. Cox-MSM will additionally adjust for the main exposure of PCV13 as a time-varying covariate. Patients who have evidence of RZV before the six-month baseline period will be excluded from the negative control exposure analysis.

Weighted 95% CIs for the VEs that exclude 0% would suggest the presence of residual confounding in the weighted models between PCV13 and the study outcomes. If so, the results for the main outcomes may be corrected for bias identified from the negative control outcome.

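### No all-cause pneumonia definition or sensitivity analysis leaves out COVID-19 pneumonia (J12.82), so a change in all-cause VE across the follow-up windows could partly reflect COVID-19

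*Protocol*

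**What the plan says.** All-cause pneumonia is the third primary objective (Protocol section 8). Its code list, Protocol Appendix Table 4 and SAP Table 7.4, contains J12.82, "Pneumonia due to coronavirus disease 2019". The one sensitivity analysis of this outcome (Protocol 9.7) removes causes characteristic of HIV. Its list, Protocol Table 11 and SAP Table 7.6, still contains J12.82.

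On follow-up, Protocol 9.1 states: "The end of the study will occur on the last date that administrative claims data will be available, September 30, 2022". Section 7 of the protocol justifies the outcome on the ground that the pneumococcus "is the most common bacterial cause of all-cause pneumonia".

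SAP 5.8.7 says: "To explore potential changes in VE over time, HRs may also be generated during specific time periods using piecewise Cox models". The windows are counted in days since index: 0-1079, 1080-1799 and 1800-2549. SAP 5.8.11 plans them for every study outcome. Calendar time enters the models only through the year of the first HIV code and an October-April season flag (SAP Table 5.3).

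Some planned analyses bear on the question indirectly:
- IPD, pneumococcal pneumonia and the two secondary outcomes have no J12.82 row, although the unspecified-causes list does hold J12.9, "Viral pneumonia, unspecified".
- SAP 5.8.12 plans a negative control exposure analysis giving "95% CIs of RZV on each of the study outcomes of interest", along with negative control outcomes.
- VE by year of HIV diagnosis is planned if feasible, restricted to days 0-1079, with 2014 as its own stratum (SAP 5.2.3 and Table 5.3).

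**The concern.** The windows exist to show whether VE changes with follow-up. Because they run from index and everyone's data stop on the same calendar date, later windows fall later in the calendar. If COVID-19 pneumonia is common in that period and PCV13 does not affect it, it adds events that pull the all-cause hazard ratio toward 1, most strongly in the last window. A reader could take the resulting fall for loss of protection. If vaccinated people differ in COVID-19 risk for reasons the weights miss, the shift could go the other way. Adjusting for diagnosis year or season does not remove this mixing of causes. The protocol's own reason for the outcome is the pneumococcal share of pneumonia, and that share would be smaller while COVID-19 pneumonia is common.

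**Working it through.** **Dates.** The earliest first HIV code is January 1, 2014. Six months of baseline puts the earliest index at about July 1, 2014.
- Earliest 5-7 year window: days 1800-2549, which is June 5, 2019 to June 23, 2021. Of its 750 days, 270 precede March 2020. For an index after March 27, 2015, none do.
- 2014 stratum: latest index about June 30, 2015; day 1079 is June 13, 2018.
- 2015-2016 stratum: latest index about June 30, 2017; day 1079 is June 13, 2020, so nearly free of COVID-19 time.

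**Share of person-time after onset (f).** The onset date and entry pattern are not in the documents and are assumed. I used a daily sum for entry all in the first year or uniform from July 2014 to June 2022, censoring of 4% or 10% a year (Protocol 9.5), with and without depletion by first events at 5,487 per 100,000.

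| Window | First-year entry, after Feb 2020 | Uniform entry, after Feb 2020 |
|---|---|---|
| 0-3 y | 0% | about 38% |
| 3-5 y | about 1.5% | about 59% |
| 5-7 y | about 85% | about 94% |

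With onset at January 2021 the 5-7 year share is about 44% (first-year) to 73% (uniform).

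**Dilution.** Let p be the assumed COVID-19 share of post-onset events, added to a constant rate of other pneumonia, with hazard ratio 1 for PCV13 on COVID-19. Then

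VE read = VE / (1 + f × p/(1 − p)).

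At 5-7 years, for VE 15%:
- February 2020, p = 20%: 15/(1 + 0.85 × 0.25) = 12.4; 15/(1 + 0.94 × 0.25) = 12.1.
- February 2020, p = 30%: 15/(1 + 0.85 × 0.4286) = 11.0; 15/(1 + 0.94 × 0.4286) = 10.7.
- January 2021, p = 20%: 15/(1 + 0.44 × 0.25) = 13.5; 15/(1 + 0.73 × 0.25) = 12.7.

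With February 2020 onset the three windows read 15.0/14.9/12.4 (first-year) or 13.7/13.1/12.1 (uniform) at p = 20%, and 15.0/14.9/11.0 or 12.9/12.0/10.7 at p = 30%. The overall VE reads 14.0-14.3 or 13.3-13.4 at 20%, and 13.3-13.8 or 12.3-12.5 at 30%.

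At the lower end of the protocol's range, VE 5%, the 5-7 year reading with February 2020 onset is 5/1.2125 = 4.1 down to 5/1.403 = 3.6.

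**Direction.** If the COVID-19 hazard ratio were 0.8, the 5-7 year reading for VE 15% would be 15.9-16.4 (February 2020 onset), a rise.

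**Precision of the 5-7 year window.** SE of log HR = √(1/d1 + 1/d0), with d1 vaccinated and d0 unvaccinated events, and a vaccinated share of person-time of 16% or 32% (assumed; 32% is the ever-vaccinated figure). Example: 7,300 events and a 16% share give d1 = 7,300 × (0.16 × 0.85)/(0.16 × 0.85 + 0.84) = 1,017 and d0 = 6,283. The SE is 0.0338 and the 95% CI is 9.2 to 20.4. Across cases the CI around 15% runs from 9.2-20.4 to 11.9-18.0 (first-year, about 7,300-15,100 events) and from 4.1-24.7 to 9.2-20.5 (uniform, about 2,100-4,400 events). Every 20% reading is inside. The 30% reading falls outside only in some first-year cases. Weights and robust standard errors are not modelled, so real intervals would probably be wider.

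**Mycoplasma.** Protocol 9.7 gives cytomegalovirus, mycobacteria and fungi as examples of excluded causes. Compared with Table 4, Table 11 lacks the rows for 484.1 (cytomegalic inclusion disease), 484.6 (aspergillosis), 484.7 (other systemic mycoses), 136.3 (pneumocystosis) and also 483/J15.7, *Mycoplasma pneumoniae*. Mycoplasma is not a mycobacterium, and Table 4 has no mycobacterial row that could have been removed. SAP Table 7.6 has the same omission.

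**The case against.** The outcome is all-cause on purpose and J12.82 is listed openly, so its inclusion cannot be called an error. The windows are conditional, and four other outcomes without the code are planned in the same windows. The size is modest: at VE 5% the shift is at most about 5 − 3.6 = 1.4 points, and under uniform entry the early window is diluted too, which flattens any trend. The result also moves with the assumed onset date. All of this stands, and it limits the point to interpretation.

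A reader might infer that the plan yields no COVID-free all-cause VE at all. The documents do not support that, because the 2014 stratum would give one for years 0-3 if feasible. It cannot supply the overall, 3-5 or 5-7 year figures. Nor can the other cross-checks: the other outcomes are different endpoints, and the negative controls test confounding rather than dilution.

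A reader might also infer that removing J12.82 would let a late fall be called waning. It would not. The windows count time since index while vaccination is time-varying (SAP 5.5), so someone vaccinated in year five contributes recently vaccinated time to the 5-7 year window.

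**Conclusion.** The gap is real and inexpensive to close: no all-cause definition or sensitivity analysis excludes J12.82, and most 5-7 year person-time falls late in the calendar. A change in all-cause VE across windows, and less so the overall VE, could therefore partly reflect COVID-19.

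It would be tempting to say that the late-window VE is biased downward. The documents give no COVID-19 share, hazard ratio or onset date, so neither direction nor size is known. The illustrative 11-13.5% at 5-7 years for a constant VE of 15% rests on assumed shares of 20-30%, no PCV13 effect on COVID-19, onset between February 2020 and January 2021, and assumed entry patterns. This is a risk of misreading a trend, not a demonstrated material bias.

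The Mycoplasma mismatch is a separate minor correction. The rule is worded as examples, so the exclusion may be intended, but no reason is given.

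**What to change.** Keep the primary definition and add to the SAP:
1. An all-cause sensitivity analysis without J12.82, overall and by window. The cost is one further run on existing data and somewhat wider intervals. If it removed 30% of post-February-2020 events, the approximate 5-7 year CI around 15% would run from 8.3-21.2 to 11.4-18.5 (first-year entry) or from 2.0-26.3 to 8.1-21.4 (uniform).
2. Optionally, an all-cause run censored before the pandemic, to support the overall, 0-3 and 3-5 year estimates only. It would also cover any COVID-19 pneumonia recorded under J12.89 or J12.9, which stay in the list; the documents do not say whether this happened. With a February 2020 cut-off it leaves only about 1,100-2,100 (first-year) or 140-260 (uniform) events at 5-7 years, with a CI as wide as −37 to 47, so it cannot settle that window.
3. A sentence stating that any late change in all-cause VE will be read against these runs and the outcomes without J12.82, and that the windows measure time since index, not time since vaccination.

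Separately, restore 483/J15.7 to Protocol Table 11 and SAP Table 7.6, or state why Mycoplasma is excluded. This costs one code-list check.
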